#### Adverse events in users or other persons

- For any AE in users or other persons the Adverse Event (AE) Documentation Form for Users / Other Persons must be completed according to the Instructions for Completion.
- If the AE fulfills one of the criteria for seriousness the SAE Report Form must be completed, additionally and reporting responsibilities have to be fulfilled (see section 14.5).
- If the AE is related to a device deficiency, the corresponding Device Deficiency Form has to be completed, too (see section 14.9).

#### 14.4 AE assessment

All AEs will be assessed in terms of seriousness, intensity, relationship to the device or clinical investigation procedures, and outcome.

#### 14.4.1 Seriousness

The seriousness of an AE is assessed by comparing AE features against the SAE definition provided in section 14.1.

#### 14.4.2 Intensity

The intensity of an AE will be graded as follows:

**Mild**: The AE is easily tolerated and does not interfere with daily activity.

Moderate: The AE interferes with daily activity, but the subject is still able to function.

Severe: The AE is incapacitating and/or requires medical intervention.

#### 14.4.3 Causality

The investigator is obligated to estimate the relationship between each AE/SAE and the test device, the comparator device or clinical investigation procedure. Clinical judgement should be used and relevant documents like Instructions for Use or Investigator's brochure consulted.

The presence of confounding factors, such as concomitant treatment, the natural history of the underlying disease, other concurrent illness or risk factors shall also be considered.

For the final analysis all AEs assessed with the relationship "possible", "probable" or "causal relationship" will be classified as "related".

The relationship should be determined using one of the following causality levels:[45]

Causal relationship:	The AE/SAE is associated with the test device, comparator device or with procedures beyond reasonable doubt when:		
	
 
the event is a known side effect of the product category the device belongs to or of similar devices and procedures
 
the event has a temporal relationship with the device use/application or procedures
 
the event involves a body-site or organ that 
 
the devices or procedures are applied to
 
the devices or procedures have an effect on
 
 
 
the event follows a known response pattern to the medical device (if the response pattern is previously known);
 
the discontinuation of medical device application (or reduction of the level of activation/exposure) and reintroduction of its use (or increase of the level of activation/exposure), impact on the event (when clinically feasible)
 
other possible causes (e.g. an underlying or concurrent illness/ clinical condition or/and an effect of another device, drug or treatment) have been adequately ruled out
 
harm to the subject is due to error in use and/or
 
the event depends on a false result given by the investigational device used for diagnosis, when applicable
 
		
	be met at the same time, depending on the type of device/procedures and the event.		
Probable:	The relationship with the use of the test or comparator device, or the relationship with procedures, seems relevant and/or the event cannot be reasonably explained by another cause.		
Possible:	The relationship with the use of the test or comparator device, or the relationship with procedures, is weak but cannot be ruled out completely.		
	Alternative causes are also possible (e.g. an underlying or concurrent illness/ clinical condition or/and an effect of another device, drug or treatment).		
	Cases where relatedness cannot be assessed, or no information has been obtained should also be classified as possible.		
Not related:	Relationship to the test device, comparator device or procedures can be excluded when:		
	
 
the event has no temporal relationship with the use of the device, or the procedures related to application of the device
 
the event does not follow a known response pattern to the medical device (if the response pattern is previously known) and is biologically implausible
 
the discontinuation of medical device application or the reduction of the level of activation/exposure - when clinically feasible - and reintroduction of its use (or increase of the level of activation/exposure), do not impact on the event
 
		

• the event involves a body-site or an organ that cannot be affected by the device or procedure

- the event can be attributed to another cause (e.g. an underlying or concurrent illness/ clinical condition, an effect of another device, drug, treatment or other risk factors)
- the event does not depend on a false result given by the device used for diagnosis, when applicable

Note: In order to establish the non-relatedness, not all the criteria listed above might be met at the same time, depending on the type of device/procedures and the serious adverse event.

#### 14.4.4 Outcome assessment

The outcome of an AE will be assessed as follows:

Recovered / Resolved:	The subject has fully recovered from the event.
Not recovered / resolved (Ongoing):	The subject has not recovered from this event.
Recovering / Resolving:	The subject is recovering from the event.
Recovered / Resolved with sequelae:	The subject is experiencing the aftereffects of a condition or injury (sequelae).
Fatal (Death):	The subject died due to this event.
Unknown:	The outcome of this event is unknown

## 14.5 AE/SAE and pregnancy reporting requirements

#### 14.5.1 General AE/SAE reporting requirements

Note: For any AE (including a SAE) all appropriate sections of the eCRF must be completed.

Any SAE must be reported by the investigator to **the sponsor's representative immediately but not later than 24 hours** of awareness **of the event via Email**. Contact details will be provided in a separate manual.

This also applies to serious and non-serious AESIs (see section 14.1 for definition), any other embolic event (regardless of seriousness and / or relationship to device or procedure), and any significant AE, which in the investigator's opinion could affect the safety of the subjects taking part in the investigation or the conduct of the investigation.

In general, information about an SAE will be collected and recorded on the SAE Reporting Form. The SAE Reporting Form will be provided by the sponsor's representative to the investigational sites and will contain additional process information for how to report.

The investigator will be requested to supply as much detailed information as possible regarding the SAE that is available at the time of the initial contact. The investigator should also complete missing or requested information and submit follow-up reports until the SAE has resolved or, in the case of permanent impairment, until the SAE has stabilized.

The sponsor's representative will inform the sponsor about any SAEs immediately after becoming aware of the respective SAE report from the investigator.

Should an SAE occur after the final visit, which is considered at least possibly related to the device or procedure, such events should always be reported to CROMA-PHARMA GmbH or its representative, even after the end of the clinical investigation.

At the end of the clinical investigation, a reconciliation of all reported SAEs will take place and be enclosed as a list in the Clinical Investigation Report.

For further information on reporting and notification requirements per country for Investigators see sections below.

Detailed reporting by the sponsor or sponsor's representative to IRBs/ECs, all Investigators and regulatory authorities will follow pertinent national legislation described in detail in Safety Management Plan (SMP).

Signals from adverse events or device deficiencies that might indicate a serious (public) health threat (see section 14.1) can be detected by either the sponsor or principal investigator but will be evaluated by the sponsor / sponsor 's representative. If required, occurrence of a serious (public) health threat will be reported according to regulatory requirements.

## 14.5.2 Serious Adverse Events (SAE) and Serious Adverse Device Effects (SADE) reporting

The investigator must report any SAE/SADE to the sponsor's representative immediately but not later than 24 hours of awareness of the event via Email.

The sponsor will report the results of UADE evaluation to all investigators, to the reviewing IRBs and to the respective competent authority (FDA) within ten working days after receipt of the first notice of the effect.

## 14.5.3 *Reporting of visual disturbances*

For reports received by the sponsor's representative containing any event relating to incidences of visual disturbances, the following information must be urgently requested.

The request will be made in the form of a query to the site (by using the 'Device Safety Query for Additional Information' form):

- Depth of injection (i.e., subcutaneous or supraperiosteal)
- The injection volume
- The symptoms that were observed
- The time to event onset, and resolution
- Any interventions that were implemented
- The symptoms that were observed
- The time to event onset, and resolution
- Any interventions that were implemented

If a response to the aforementioned queries is not received **within 24 hours**, a follow-up reminder will be sent, and the queries escalated to the Medical Monitor and Project Manager at the sponsor's representative.

#### 14.5.4 AESIs and other embolic events reporting

All AESI (serious and non-serious) and any other embolic event (regardless of seriousness and / or relationship to device or procedure) have to be reported by the investigator to **the sponsor's representative within 24 hours** of awareness **of the event via Email using the SAE Reporting Form.** 

The sponsor's representative will report all AESIs and any other embolic event (regardless of seriousness and / or relationship to device or procedure) to the respective competent authority (FDA) in an expedited manner (see sections 14.5.1 to 14.5.3).

#### 14.5.5 Pregnancy

Any pregnancy must be notified to the contact given above within the same timelines as an SAE (within 24 hours after being made aware of the pregnancy). The Pregnancy and Lactation Exposure Form will be provided by the sponsor's representative to the investigational sites and will contain additional process information for how to report. If pregnancy is associated with an SAE (e.g., if the mother is hospitalized for hemorrhage), a separate SAE Reporting Form must be filed in addition to Pregnancy and Lactation Exposure Form. The pregnant subject must be withdrawn immediately from further treatment, if applicable. The pregnant subject may remain in the study for safety assessments during the scheduled study visits.

## 14.6 AE/SAE and pregnancy follow-up

The investigator will take all appropriate and necessary measures required for resolution of the AE.

All AEs must be followed-up by the investigator until recovery, or until the investigator determines that the subject's condition is stable, or subject's last day of the clinical investigation at the site, whichever occurs first. All subjects excluded from repeat-treatment should continue to be followed until the resolution of all ongoing, related AEs.

All SAEs/AESIs judged to be related to the device (SADEs) must be followed by the investigator until the subject has recovered, recovered with sequelae, died, or until the investigator determines that the subject's condition is stable, whichever occurs first.

In addition, those subjects who have a related AE ongoing (i.e., not recovered / not resolved) and not stabilized (i.e., recovering / resolving) after 24 weeks after last injection of the repeat-treatment phase will be followed for a longer follow-up outside the investigation. The follow-up for these subjects would continue until resolution (i.e., recovered / resolved) or stabilization of the condition (i.e., recovered / resolved) resolved with sequelae).

AEs to be followed outside the investigation will be reported to the sponsor's vigilance department using the Post-Study-AE-Follow-Up Form. Contact details and additional process information for how to report will be given on the respective form.

Any pregnancy must be followed-up until the pregnancy outcome at least once in each trimester and pregnancy outcome (including pregnancy duration and health status of a newborn or cause of premature termination, as applicable) will be reported to the sponsor's representative using a Pregnancy Query Form for the status of pregnancy. If it is still on-going at the end of the clinical investigation, follow-up will be continued outside of the context of clinical investigation.

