# 6.3.6 Withdrawal criteria and procedures

The subject **MUST** be withdrawn from the investigation for any of the following reasons:

1. Withdrawal of consent: At any time during the investigation and without giving reasons, a subject may decline to participate further. The subject will not suffer any disadvantage as a result.

The subject **MAY** be withdrawn from the investigation for any of the following reasons:

- 1. Occurrence of an AE which requires a premature termination of the treatment or precludes followup of the subject (e.g., COVID-19)
- 2. A major CIP deviation, which may interfere with evaluation of the treatment outcome (e.g., additional aesthetic correction of the defect during the course of the investigation, use of prohibited medication, or similar)
- 3. Investigator's decision, triggered by safety, behavioural or administrative reasons
- 4. Pregnancy; **Note:** pregnant women **must** be withdrawn from **further treatment**; However, pregnant women may remain in the study for safety assessments during the scheduled study visits.
- 5. Subjects with abnormal clinically significant changes in visual examination after treatment **must** be withdrawn from **further treatment** in case an eye specialist confirms that the result is related to a vascular injection of the dermal filler (see section 6.4.8 and section 16.1).

The subjects may remain in the study at least for safety assessments during the scheduled study visits.

6. Subjects who experience neurological symptoms indicative of a vaso-occlusional event after treatment **must** be withdrawn from **further treatment** in case a neurologist confirms that the result is related to a vascular injection of the dermal filler (see section 6.4.9, also see section 16.1).

The subjects may remain in the study at least for safety assessments during the scheduled study visits.

Reasons, circumstances and findings related to early withdrawal should be fully described in the subject's source records and the eCRF respecting the subject's rights.

Attempts should be made to perform an early termination visit, which should consist of the assessments planned for Visit 9 (SV1), Visit SV2 to SV4 or Visit RT5 (depending on the study phase) – also see section 6.5.16. In the event that the withdrawal is caused by an AE, the procedures stated in section 14 must be followed.

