## Optional repeat-treatment phase including screening phase for repeat-treatment

- Subjects who enter the screening phase for optional repeat-treatment and
  - who are not eligible for the repeat-treatment phase and who are not treated for any reason during repeat-treatment phase will be considered as screening failures for repeat-treatment (SV1, SV2, SV3, SV4, RT1)
  - who are eligible but do not participate in the optional repeat-treatment phase will be considered as completer (initial treatment phase)
- Subjects who prematurely discontinue the investigation after receiving at least one dose of the device at Visit RT1 will be defined as withdrawals / dropouts.

• Subjects who complete the repeat-treatment phase (incl. Visit RT 5) are defined as completer (repeat-treatment phase).

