## 6.4.20 Safety monitoring

The safety of the subjects will be monitored throughout the investigation, from Screening (Visit 1) until their End of Study visit. The follow-up period will be prolonged outside the investigation, if a related AE

is ongoing and not stabilized after 24 weeks after last injection of the repeat-treatment phase (see section 14.6 for details).

The subjects will be instructed to immediately contact the investigator by phone in case of occurrence of any untoward event between the visits (including visual examinations after treatment visits).

In order to identify potential AEs immediately post-administration a safety evaluation 15 min after each treatment needs to take place. Furthermore, subject diaries will be provided to the subjects, and they will be instructed to note injection site reactions, and symptoms of interest (see section 6.4.19).

Any subject with an (S)AE or clinically significant abnormal test result will be evaluated by the treating investigator and will be treated and/or followed up as per local clinical practice. Where appropriate, medical tests and examinations may be performed to ensure that an AE has fully resolved.

The procedure for collection, recording and reporting of AEs and device deficiencies is described in section 14. Device deficiencies will be documented as well at each device treatment (see section 14.9).

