## 14.3 AE/SAE documentation

For each AE the following must be reported:

- Description of the event (event term)
- Seriousness
- Start date
- Intensity
- Action taken with subject (none, medical and/or surgical / non-pharmaceutical procedure)
- Action taken with device (none [no action taken], device withdrawn [no touch-up treatment(s) / repeat-treatment due to AE], device interrupted [touch-up treatment(s) / repeat-treatment later than required by study design due to AE or injection interrupted due to AE during treatment session])
- Outcome
- End date (if applicable)
- The relationship to the device and procedure, respectively

The information will be documented in subject's source record and in the eCRF.

Each AE and any new information concerning these events has to be documented, even if the investigator feels that it is not connected with the device or procedure.

The AE will be described in precise, standard medical terminology. The investigator will attempt to establish a diagnosis of the event based on signs, symptoms, and/or other clinical information (including affected body site(s)). In such cases, the diagnosis will be documented as the AE and not the individual

signs/symptoms. In case of any injection site reaction the exact location (e.g., upper or lower lips) should be clearly noted.

Each AE should be reported separately. The investigator will record all AEs in subject's (medical) record and on the "Adverse Events" page of the eCRF. For SAEs, the "Serious Adverse Event Reporting Form" must also be completed. Complete description of all AEs should be also available in source documents of the subject.

Adverse events will be documented beginning after provision of informed consent until the last visit of the subject. The follow-up period will be prolonged outside the investigation, if a related AE is ongoing and not stabilized after 24 weeks after last injection of the repeat-treatment phase (see section 14.6 for details).

AEs initially observed during or after baseline treatment are defined as treatment-emergent AEs (TEAEs). AEs occurring after informed consent but before baseline treatment will be defined as non-TEAEs. Any medical condition that is present prior to day of screening should be considered as medical history (i.e., concomitant disease) and not recorded as an AE. If such condition, however, deteriorates after the device administration, at any time during the investigation, it should be reported as an AE.

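### For a subject treated at RT1 who leaves before Week 24 of the repeat phase, section 14.6 ends follow-up of an open, non-serious related AE on the last study day, in conflict with section 6.1.1 and the synopsis

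*Protocol*

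**What the plan says.** Section 14.6 of the protocol gives a general rule and three extensions.

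- **General rule.** Every AE is followed until recovery, until the investigator judges the condition stable, "or subject's last day of the clinical investigation at the site, whichever occurs first".
- **Extension 1.** "All subjects excluded from repeat-treatment should continue to be followed until the resolution of all ongoing, related AEs".
- **Extension 2.** SAEs and AESIs judged related to the device are followed to recovery, recovery with sequelae, death or a stable condition. There is no cut-off at the last study day.
- **Extension 3.** Related AEs that are ongoing and not stabilised 24 weeks after the last repeat-phase injection are followed outside the investigation to resolution or stabilisation. The route is stated: "AEs to be followed outside the investigation will be reported to the sponsor's vigilance department using the Post-Study-AE-Follow-Up Form".

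Section 14.3 repeats the third trigger ("if a related AE is ongoing and not stabilized after 24 weeks after last injection of the repeat-treatment phase"), and section 6.4.20 does so in nearly the same words ("is ongoing and not stabilized after 24 weeks after last injection of the repeat-treatment phase"). Both refer to 14.6 for details.

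The visit overviews in the synopsis and section 6.1.1 say something different. After describing the telephone contacts, they state that AEs resulting from device injection are closely followed until they resolve. They give no cut-off at the last study day and no limit by phase.

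Section 6.3.11 provides for the subjects at issue: "Subjects who prematurely discontinue the investigation after receiving at least one dose of the device at Visit RT1 will be defined as" withdrawals or dropouts.

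**The concern.** The third extension is tied to a time point that a subject leaving at or after RT3 or RT4 has not reached, and the first covers only subjects who were not retreated. An RT1-treated early leaver therefore seems to fall between them.

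The resulting order of protection is the wrong way round. A completer of RT5, already observed for 24 weeks after the last injection, gets extended follow-up for an open related AE. A subject excluded from repeat-treatment is followed until all related AEs resolve. A subject who received the repeat injection and left after 4 or 12 weeks has neither.

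The rationale given with Amendment 1 (cited here only for purpose) was that repeat-phase follow-up is 24 weeks against 48 weeks after initial treatment. A shorter observation period was the reason for the extension, and early leavers have the shortest.

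What is at stake is whether a site must keep contact with such a subject and report the outcome. The primary endpoint, sample size and error rate are not touched.

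**Working it through.** **Case tested:** a subject injected at RT1, with a related AE that is neither serious nor an AESI and is open and not stabilised, who leaves before Week 24 of the repeat phase.

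**Clauses of 14.6 against the case**

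| Clause | Applies? | Reason |
|---|---|---|
| General rule | Yes | Ends on the last study day, the earliest of its three end points here |
| Extension 1 (excluded from repeat-treatment) | No | The subject received repeat-treatment |
| Extension 2 (related SAE/AESI) | No | The event is neither |
| Extension 3 (open after 24 weeks) | Not at exit | The subject leaves before that time |

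**Other sections**

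- 14.3 and 6.4.20 use the same trigger and point back to 14.6.
- 6.3.6 refers AE-caused withdrawals to section 14, so it adds no separate duty.
- 6.5.16 provides one early termination visit with RT5 assessments and states nothing after it.
- 6.4.20 says a subject with an AE "will be treated and/or followed up as per local clinical practice", and that tests may be done to confirm full resolution. This is permissive and gives no reporting route to the sponsor.
- 14.5.1 covers events arising after the final visit for SAEs only.
- 6.1.1 and the synopsis say until resolution. For the case tested this contradicts the general rule in 14.6.

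**Can a reachable subject be in this group?** Yes. Section 6.3.6 lists, besides withdrawal of consent, "Investigator's decision, triggered by safety, behavioural or administrative reasons" as a ground for withdrawal.

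**Not affected.** Subjects who leave in the initial phase are barred from repeat-treatment by inclusion criterion 2 and exclusion criterion 20 in section 6.3.5, so on a natural reading extension 1 covers them.

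**Size.** The protocol states no expected number, so this is an illustration.

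- Estimated to qualify for repeat-treatment: about 300 (section 6.3.1). Assume all are treated.
- Leaving before RT5: 5% to 10%, assumed. 300 × 0.05 = 15; 300 × 0.10 = 30.
- Related AEs after repeat-treatment: 14/167 = 8.4% (Table 11, for the comparator, so a proxy).
- Ceiling, every such AE still open at exit: 15 × 0.084 = 1.3; 30 × 0.084 = 2.5.
- Half open at exit (assumed, since section 4.2.2 says most of those AEs resolved within three months): 1.3 / 2 ≈ 0.6; 2.5 / 2 ≈ 1.3.
- Lower attrition, from VINO, where 61 of 62 completed (same device, different indication): 1/62 = 1.6%; 300 × 0.016 ≈ 5 leavers; 5 × 0.084 ≈ 0.4, before removing AEs already resolved.

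Consent withdrawals, losses to follow-up and AEs judged stable reduce all of these.

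**The case against.** The strongest reply is that the protocol already requires the follow-up. Section 6.1.1 and the synopsis promise it until resolution for injection-related AEs, and 14.6 opens with a duty to take the measures needed for the AE to resolve. So a reader who infers that the protocol provides nothing for these subjects goes too far. What stands is a conflict: 14.6 is the dedicated rule, and it names an earlier stopping point. The overview sentence sits beside the 24 to 48 hour telephone contacts and is not carried into 14.6.

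Second, extension 3 need not require attendance at RT5. It can be read by calendar time, so that a leaver whose AE is still open 24 weeks after injection qualifies. That reading is fair and narrows the gap to the interval between exit and Week 24. It does not close it, because no contact is required in that interval to establish the AE's status at Week 24.

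Third, the group is small. Withdrawal of consent is the only mandatory ground in 6.3.6, and those subjects cannot be obliged to return. Pregnant subjects and those with confirmed visual or neurological events stop treatment but may stay for safety visits. This holds, and it is why the point is minor.

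Fourth, a persistent lump in a subject leaving at RT3 would be a poor example. A listed injection site reaction becomes an AE only when it lasts more than 28 days (section 14.1, Note 2), and RT3 falls at Week 4 ± 5 days. An unchanged lump might also be judged stable, which properly ends follow-up. A leaver around RT4 with a reaction that is still changing fits better.

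A reader might also infer that related SAEs or AESIs go unfollowed, or that the safety analysis is biased. Neither is supported: extension 2 covers the former, and post-study follow-up goes to the sponsor's vigilance department, outside the planned analyses.

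**Conclusion.** The point holds in limited form. For an RT1-treated subject who leaves before Week 24 with an open, unstable related AE that is neither serious nor an AESI, 14.6 ends follow-up on the last study day or, on the reading most favourable to the plan, requires none between exit and Week 24. This contradicts 6.1.1 and the synopsis and gives early leavers less protection than completers or subjects excluded from repeat-treatment.

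Severity is minor. The realistic expectation is about 0 to 1 subject, with a ceiling of 3 (2.5 rounded up). These figures rest on assumed attrition of 5% to 10%, on all of the roughly 300 qualifying subjects being treated, and on a comparator AE rate. The reading of the clauses does not depend on them. The consequence is for individual patient safety only.

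**What to change.** In 14.6, 14.3 and 6.4.20, replace the 24-week trigger with: a related AE ongoing and not stabilised at the subject's last study visit in the repeat-treatment phase, including early termination and subject to consent, is followed to resolution or stabilisation and reported on the existing Post-Study-AE-Follow-Up Form.

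Leave the clause for subjects excluded from repeat-treatment as it is. It runs to resolution, and merging it into the new trigger would weaken it. Align the overview sentence in 6.1.1 and the synopsis with 14.6, so that sites have one end point to follow.

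The cost is one sentence in three sections, two aligned overview sentences, and occasional extra contacts for very few subjects. No new form and no change to any analysis is needed.
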